15.3 Safety

15.3.1 Tables

Number	Title	Population	Data Point Set	Programming notes
14.3.1.1.1	Overview of TEAEs	Safety	SDPS2	Include in TLR
14.3.1.1.2	Summary of TEAEs by System Organ Class and Preferred Term	Safety	SDPS2	Include in TLR
14.3.1.2	Summary of Related TEAEs by System Organ Class and Preferred Term	Safety	SDPS2	Include in TLR
14.3.1.3	Summary of TEAEs of CTCAE Grade 3 or Above by System Organ Class and Preferred Term	Safety	SDPS2	
14.3.1.4	Summary of Non-serious TEAEs Reported by at Least 5% of Participants in Any Treatment Group by System Organ Class and Preferred Term	Safety	SDPS2	
14.3.1.5	Summary of Serious TEAEs by System Organ Class and Preferred Term	Safety	SDPS2	
14.3.1.6	Summary of Fatal TEAEs by System Organ Class and Preferred Term	Safety	SDPS2	
14.3.1.7	Summary of TEAEs Leading to Permanent Discontinuation from Study Treatment by System Organ Class and Preferred Term	Safety	SDPS2	
14.3.4.1.1	Summary of Haematology Parameters	Safety	SDPS1	
14.3.4.1.2	Shifts from Baseline to Worst-case Post-Baseline with Respect to the Normal Range for Haematology Parameters	Safety	SDPS2	
14.3.4.1.3	Shifts from Baseline to Worst-case Post-Baseline with Respect to the PCI Criteria for Haematology Parameters	Safety	SDPS2	
14.3.4.2.1	Summary of Haematology Parameters	Safety	SDPS1	
14.3.4.2.2	Shifts from Baseline to Worst-case Post-Baseline with Respect to the Normal Range for Chemistry Parameters	Safety	SDPS2	

Number	Title	Population	Data Point Set	Programming notes
14.3.4.2.3	Shifts from Baseline to Worst-case Post-Baseline with Respect to the PCI Criteria for Chemistry Parameters	Safety	SDPS2	
14.3.5.1	Summary of ECG Parameters	Safety	SDPS1	
14.3.5.2	Shifts from Baseline to Worst-case Post-Baseline with Respect to the PCI Criterion for QTcF	Safety	SDPS2	
14.3.6.1	Summary of Vital Signs	Safety	SDPS1	
14.3.6.2	Shifts from Baseline to Worst-case Post-Baseline with Respect to the PCI Criterion for Vital Signs	Safety	SDPS2	

15.4 Data Listings

Number	Title	Population	Data Point Set	Programming notes
16.2.1.1	Reasons for Screen Failure	Enrolled	SDPS2	
16.2.1.2	End of Treatment Disposition	FAS	SDPS2	
16.2.1.3	End of Study Disposition	FAS	SDPS2	
16.2.1.4	Participants for Whom the Blind Was Broken	FAS	SDPS2	
16.2.1.5	Planned and Actual Treatments	FAS	SDPS2	
16.2.1.6	Visits Missed Due to COVID-19	FAS	SDPS2	
16.2.2.1	Protocol Deviations	FAS	SDPS2	
16.2.2.2	Participants Not Meeting Inclusion and Exclusion Criteria	FAS	SDPS2	
16.2.3	Participants Excluded from Any Population	Enrolled	SDPS2	
16.2.4.1	Demographics	FAS	SDPS2	
16.2.4.2	Smoking Status	FAS	SDPS2	
16.2.4.3	Baseline Disease Characteristics	FAS	SDPS2	
16.2.4.4.1	Past Atopic Dermatitis Treatment	FAS	SDPS2	
16.2.4.4.2	Current Atopic Dermatitis Treatment	FAS	SDPS2	
16.2.4.5	Medical History	FAS	SDPS2	
16.2.4.6	Prior Medications	FAS	SDPS2	

Statistical Analysis Plan
Version 2.0, Final 16-Jan-2023

EDP1815-207

Number	Title	Population	Data Point Set	Programming notes
16.2.4.7	Concomitant Medications	FAS	SDPS2	
16.2.5.1	Participant Dosing Diary	FAS	SDPS2	
16.2.5.2	Study Drug Compliance	FAS	SDPS2	
16.2.5.3	Exposure to Emollient	FAS	SDPS2	
16.2.5.4	Emollient Compliance	FAS	SDPS2	
16.2.6.1	Individual Components of the EASI Questionnaire	FAS	EDPS7	
16.2.6.2	EASI Endpoints	FAS	EDPS7	
16.2.6.3	vIGA Score	FAS	EDPS7	
16.2.6.4.1	BSA and vIGA*BSA	FAS	EDPS7	
16.2.6.4.2	vIGA and BSA Response Endpoints	FAS	EDPS7	
16.2.6.5	Individual Components of the SCORAD Questionnaire	FAS	EDPS7	
16.2.6.6	SCORAD Endpoints	FAS	EDPS7	
16.2.6.7	DLQI Items and Score	FAS	EDPS7	
16.2.6.8	PP-NRS and SD-NRS Scores	FAS	EDPS7	
16.2.6.9	POEM Items and Score	FAS	EDPS7	
16.2.6.10	Topical Corticosteroid or Calcineurin Inhibitors	FAS	EDPS7	
16.2.6.11	Topical Antimicrobial or Systemic Antibiotic Rescue Therapy	FAS	EDPS7	
16.2.6.12	Rescue Therapy Endpoints	FAS	EDPS7	
16.2.6.13	PP-NRS and SD-NRS Time to Event Endpoints	FAS	EDPS1	
16.2.6.14	SF-12 Individual Components and Scores	FAS	EDPS7	
16.2.6.15	HADS Individual Components and Scores	FAS	EDPS7	
16.2.6.16	ADCT Individual Components and Scores	FAS	EDPS7	
16.2.7	Inclusion/Exclusion of Participants Data from Analysis	FAS	EDPS7	
16.2.7.1.1	Adverse Events	Safety	SDPS2	
16.2.7.1.2	Serious Adverse Events	Safety	SDPS2	
16.2.7.1.3	Fatal Adverse Events	Safety	SDPS2	
16.2.7.1.4	Adverse Events Leading to Treatment Discontinuation or Early Termination of the Study	Safety	SDPS2	

Statistical Analysis Plan
Version 2.0, Final 16-Jan-2023

EDP1815-207

Number	Title	Population	Data Point Set	Programming notes
16.2.7.2.1	Haematology parameters	Safety	SDPS2	
16.2.7.2.2	Haematology parameters PCI	Safety	SDPS2	
16.2.7.2.3	Chemistry parameters	Safety	SDPS2	
16.2.7.2.4	Chemistry parameters PCI	Safety	SDPS2	
16.2.7.2.5	Urinalysis	Safety	SDPS2	
16.2.7.3.1	ECG Data	Safety	SDPS2	
16.2.7.3.2	ECG PCI	Safety	SDPS2	
16.2.7.4.1	Vital Signs	Safety	SDPS2	
16.2.7.4.2	Vital Signs PCI	Safety	SDPS2	
16.2.7.5	Female Fertility Status and Pregnancy Test Results	Safety	SDPS2	

16 Appendix 2: Eczema Area and Severity Index

Intensity

A representative area of psoriasis is selected for each body region (head and neck, upper limbs, trunk, lower limbs).

The average severity of each of four signs (erythema/redness, edema/papulation, excoriation, lichenification) in each body region is scored as:

- 0 = None
- 1 = Mild
- 2 = Moderate
- 3 = Severe

Half points (1.5 and 2.5) may be used. 0.5 is not permitted – if a sign is present it should be at least mild.

A severity score is calculated for each body region as the sum of the four scores for erythema/redness, edema/papulation, excoriation and lichenification.

- A1 = A severity score for head and neck
- A2 = A severity score for upper extremities
- A3 = A severity score for trunk
- A4 = A severity score for lower extremities

Each subtotal is multiplied by the body surface area represented by that region as follows:

- B1 = 0.1 x A1
- B2 = 0.2 x A2
- B3 = 0.3 x A3
- B4 = 0.4 x A4

Percentage area affected

The percentage area affected by psoriasis is evaluated in each of the four body regions. In each body region the area is expressed as:

- 0 = not affected at all
- 1 = 1 – 9%
- 2 = 10-29%
- 3 = 30-49%
- 4 = 50%-69%
- 5 = 70-89%
- 6 = 90-100%

EASI score calculation

Each of the body area scores is multiplied by the severity score for the relevant body region (B1-B4) to give four area intensity scores (C1-C4).

The EASI score is the sum of the four area intensity scores:

$$\text{EASI score} = C1 + C2 + C3 + C4.$$

EASI score ranges from 0 to 72.

17 Appendix 3: Validated Investigator Global Assessment

The vIGA score is selected using the descriptors below that best describe the overall appearance of the lesions at a given time point. It is not necessary that all characteristics under Morphological Description be present.

- **0 = Clear**
No inflammatory signs of atopic dermatitis (no erythema, no induration/papulation, no lichenification, no oozing/crusting). Post-inflammatory hyperpigmentation and/or hypopigmentation may be present.
- **1 = Almost clear**
Barely perceptible erythema, barely perceptible induration/papulation, and/or minimal lichenification. No oozing or crusting.
- **2 =Mild**
Slight but definite erythema (pink), slight but definite induration/papulation, and/or slight but definite lichenification. No oozing or crusting.
- **3 = Moderate**
Clearly perceptible erythema (dull red), clearly perceptible induration/papulation, and/or clearly perceptible lichenification. Oozing and crusting may be present.
- **4 = Severe**
Marked erythema (deep or bright red), marked induration/papulation, and/or marked lichenification. Disease is widespread in extent. Oozing or crusting may be present.

The vIGA score ranges from 0 to 4.

18 Appendix 4: Severity Scoring of Atopic Dermatitis**Investigator-rated area score****Extent**

The rule of 9 is used to calculate the affected area (A) as a percentage of the whole body.

In each affected area the area involved is assessed:

	Front	Back
Head and Neck	0 to 4.5	0 to 4.5
Upper limbs (left)	0 to 4.5	0 to 4.5
Upper limbs (right)	0 to 4.5	0 to 4.5
Palms	0, 1, 2	
Trunk	0 to 18	0 to 18
Genitals	0, 0.5, 1	
Lower limbs (left)	0 to 9	0 to 9
Lower limbs (right)	0 to 9	0 to 9

The scores for each area are added together to give 'A'. It should be noted that this gives a theoretical maximum of 102% BSA.

Intensity

An intensity of each of six signs (erythema/redness, edema/papulation, oozing/crust, excoriation, lichenification, dryness) in each body region is scored as:

- 0 = Absence
- 1 = Mild
- 2 = Moderate
- 3 = Severe

The intensity scores are added together to give 'B' (maximum 18).

Subjective symptoms component

- Pruritus is measured on visual analogue scale and ranges from 0 to 10.
- Sleep loss is measured on visual analogue scale and ranges from 0 to 10.

The subjective symptoms scores are added together to give 'C' (maximum 20).

SCORAD calculation

The SCORAD score is defined as:

$$\text{SCORAD score} = A/5 + 7B/2 + C.$$

SCORAD score ranges from 0 to 103.

19 Appendix 5: Patient Oriented Eczema Measure

The POEM consists of 7 questions:

1. Over the last week, on how many days has your skin been itchy because of the eczema?
2. Over the last week, on how many nights has your sleep been disturbed because of the eczema?
3. Over the last week, on how many days has your skin been bleeding because of the eczema?
4. Over the last week, on how many days has your skin been weeping or oozing clear fluid because of the eczema?
5. Over the last week, on how many days has your skin been cracked because of the eczema?
6. Over the last week, on how many days has your skin been flaking off because of the eczema?
7. Over the last week, on how many days has your skin felt dry or rough because of the eczema?

Each question is scored as:

- 0 = No days
- 1 = 1-2 days
- 2 = 3-4 days
- 3 = 5-6 days
- 4 = Every day

If one question is left unanswered this is scored 0 and the scores are summed and expressed as usual out of a maximum of 28.

If two or more questions are left unanswered the questionnaire is not scored.

The POEM score is the sum of the 7 item scores and ranges from 0 to 28.

20 Appendix 6: Dermatology Quality of Life Index

The DLQI consists of 10 questions:

1. Over the last week, how itchy, sore, painful or stinging has your skin been?
2. Over the last week, how embarrassed or self-conscious have you been because of your skin?
3. Over the last week, how much has your skin interfered with you going shopping or looking after your home or garden?
4. Over the last week, how much has your skin influences the clothes you wear?
5. Over the last week, how much has your skin affected any social or leisure activities?
6. Over the last week, how much has your skin made it difficult for you to do any sport?
7. Over the last week, has your skin prevented you from working or studying?
If "No", over the last week how much has your skin been a problem at work or studying?
8. Over the last week, how much has your skin created problems for your partner or any of your close friends or relatives?
9. Over the last week, how much has your skin caused any sexual difficulties?
10. Over the last week, how much of a problem has the treatment for your skin been, for example by making your home messy, or taking up time?

Questions 1 and 2 is scored on a four-point Likert scale:

- 3 = Very much
- 2 = A lot
- 1 = A little
- 0 = Not at all

Questions 3-6 and 8-10 also have an option of not relevant and are scored as:

- 3 = Very much
- 2 = A lot
- 1 = A little
- 0 = Not at all
- 0 = Not relevant

Question 7 is a 2-part question and is scored as:

- 3 = Yes
- 3 = No; Very much
- 2 = No; A lot
- 1 = No; A little
- 0 = No; Not at all
- 0 = Not relevant

Any unanswered question is scored as 0.

The DLQI score is the sum of the 10 item scores.

21 Appendix 7: 12-Item Short Form Health Survey

The SF-12 consists of 12 questions:

1. In general, would you say your health is
2. Does your health now limit you in moderate activities, such as moving a table, pushing a vacuum cleaner, bowling, or playing golf? If so, how much?
3. Does your health now limit you in climbing several flights of stairs? If so, how much?
4. During the past 4 weeks, how much of the time have you had any of the following problems with your work or other regular daily activities? Accomplished less than you would like as a result of your physical health
5. During the past 4 weeks, how much of the time have you had any of the following problems with your work or other regular daily activities? Were limited in the kind of work or other activities as a result of your physical health
6. During the past 4 weeks, how much of the time have you had any of the following problems with your work or other regular daily activities? Accomplished less than you would like as a result of any emotional problems (such as feeling depressed or anxious)
7. During the past 4 weeks, how much of the time have you had any of the following problems with your work or other regular daily activities? Did work or other activities less carefully than usual as a result of any emotional problems (such as feeling depressed or anxious)
8. During the past 4 weeks, how much did pain interfere with your normal work (including both work outside the home and housework)?
9. How much of the time during the past 4 weeks have you felt calm and peaceful?
10. How much of the time during the past 4 weeks did you have a lot of energy?
11. How much of the time during the past 4 weeks have you felt downhearted and depressed?
12. During the past 4 weeks, how much of the time has your physical health or emotional problems interfered with your social activities (like visiting with friends, relatives, etc.)?

Questions 1 is scored as:

- Excellent
- Very good
- Good
- Fair
- Poor

Questions 2 and 3 are scored as:

- Yes, limited a lot
- Yes, limited a little
- No, not limited at all

Questions 4-7 and 9-12 are scored as:

- All of the time
- Most of the time
- Some of the time
- A little of the time
- None of the time

Question 8 is scored as:

- Not at all
- A little bit
- Moderately
- Quite a bit
- Extremely

PCS component is based on questions 1-5 and 8. MCS component is based on questions 6-7 and 9-12.

SF-12 MCS and PCS are calculated using Optum's PRO CoRE software and ranges from 0 to 100.

22 Appendix 8: Hospital Anxiety and Depression Scale

The HADS consists of 14 questions (7 anxiety and 7 depression):

1. I feel tense or "wound up" (*anxiety*)
2. I enjoy the things I used to enjoy (*depression*)
3. I get a sort of frightened feeling as if something awful is about to happen (*anxiety*)
4. I can laugh and see the funny side of things (*depression*)
5. Worrying thoughts go through my mind (*anxiety*)
6. I feel cheerful (*depression*)
7. I can sit at ease and feel relaxed (*anxiety*)
8. I feel as if I am slowed down (*depression*)
9. I get a sort of anxious feeling like 'butterflies' in the stomach (*anxiety*)
10. I have lost interest in my appearance (*depression*)
11. I feel restless as I have to be on the move (*anxiety*)
12. I look forward with enjoyment to things (*depression*)
13. I get sudden feelings of panic (*anxiety*)
14. I can enjoy a good book, radio or television program (*depression*)

Each question is scored on a four-point Likert scale:

Question 1:

- 3 = Most of the time
- 2 = A lot of the time
- 1 = From time to time, occasionally
- 0 = Never

Question 2:

- 0 = Definitely
- 1 = Not quite so much
- 2 = Only a little
- 3 = Hardly at all

Question 3:

- 3 = Very definitely and fairly badly
- 2 = Yes, but not too badly
- 1 = Sometimes, but it doesn't worry me
- 0 = Never

Question 4:

- 0 = As much as I always could
- 1 = Not quite so much now

Statistical Analysis Plan
Version 2.0, Final 16-Jan-2023

EDP1815-207

- 2 = Definitely not so much now
- 3 = Not at all

Question 5:

- 3 = A great deal of the time
- 2 = A lot of the time
- 1 = From time to time, but not too often
- 0 = Only occasionally

Question 6:

- 3 = Not at all
- 2 = Not often
- 1 = Sometimes
- 0 = Most of the time

Question 7:

- 0 = Definitely
- 1 = Usually
- 2 = Not often
- 3 = Not at all

Question 8:

- 3 = Nearly all the time
- 2 = Very often
- 1 = Sometimes
- 0 = Not at all

Question 9:

- 0 = Not at all
- 1 = Occasionally
- 2 = Quite Often
- 3 = Very Often

Question 10:

- 3 = Definitely
- 2 = I don't take as much care as I should
- 1 = I may not take quite as much care
- 0 = I take just as much care as ever

Question 11:

- 3 = Very much indeed
- 2 = Quite a lot
- 1 = Not very much

- 0 = Not at all

Question 12:

- 0 = As much as I ever did
- 1 = Rather less than I used to
- 2 = Definitely less than I used to
- 3 = Hardly at all

Question 13:

- 3 = Very often indeed
- 2 = Quite often
- 1 = Not very often
- 0 = Not at all

Question 14:

- 0 = Often
- 1 = Sometimes
- 2 = Not often
- 3 = Very seldom

HADS Anxiety and Depression Total Scores

The HADS anxiety total score is the sum of the 7 anxiety scores. The HADS depression total score is the sum of the 7 depression scores.

Total scores for anxiety and depression ranges from 0 to 21 and classifies as:

- 8-10 = Mild
- 11-14 = Moderate
- 15-21 = Severe

23 Appendix 9: Atopic Dermatitis Control Tool

The ADCT consists of 6 questions:

1. Over the last week, how would you rate your eczema-related symptoms (for example, itching, dry skin, skin rash)?
2. Over the last week, how many days did you have intense episodes of itching because of your eczema?
3. Over the last week, how bothered have you been by your eczema?
4. Over the last week, how many nights did you have trouble falling or staying asleep because of your eczema?
5. Over the last week, how much did your eczema affect your daily activities?
6. Over the last week, how much did your eczema affect your mood or emotions?

Questions 1 is scored as:

- 0 = None
- 1 = Mild
- 2 = Moderate
- 3 = Severe
- 4 = Very severe

Question 2 is scored as:

- 3 = Not at all
- 2 = 1-2 days
- 1 = 3-4 days
- 0 = 5-6 days
- 0 = Every day

Question 3 is scored as:

- 0 = Not at all
- 1 = A little
- 2 = Moderately
- 3 = Very
- 4 = Extremely

Question 4 are scored as:

- 3 = No nights
- 2 = 1-2 nights
- 1 = 3-4 nights
- 0 = 5-6 nights
- 0 = Every night

Questions 5 and 6 are scored as:

- 0 = Not at all
- 1 = A little
- 2 = Moderately
- 3 = A lot
- 4 = Extremely

The ADCT total score is the sum of the 6 ADCT questions and ranges from 0 to 24.

24 Appendix 10: MedDRA Internationally Agreed Order for System Organ Class

The internationally agreed SOC order to be used for medical history and AE summary tables is provided in [Table 5](#).

Table 5 MedDRA Internationally Agreed SOC Order

Order Number	System Organ Class
1	Infections and infestations
2	Neoplasms benign, malignant and unspecified (incl cysts and polyps)
3	Blood and lymphatic system disorders
4	Immune system disorders
5	Endocrine disorders
6	Metabolism and nutrition disorders
7	Psychiatric disorders
8	Nervous system disorders
9	Eye disorders
10	Ear and labyrinth disorders
11	Cardiac disorders
12	Vascular disorders
13	Respiratory, thoracic and mediastinal disorders
14	Gastrointestinal disorders
15	Hepatobiliary disorders
16	Skin and subcutaneous tissue disorders
17	Musculoskeletal and connective tissue disorders
18	Renal and urinary disorders
19	Pregnancy, puerperium and perinatal conditions
20	Reproductive system and breast disorders
21	Congenital, familial and genetic disorders
22	General disorders and administration site conditions
23	Investigations
24	Injury, poisoning and procedural complications
25	Surgical and medical procedures
26	Social circumstances
27	Product issues

25 Appendix 11: Safety Laboratory Evaluations

Table 6 Safety Laboratory Parameters and Units

Category	Parameter	Conventional Unit	SI Units	PCI Criteria (SI units)	
				Low	High
Haematology	Hemoglobin	g/dL	g/L	<100 ≥20 decrease from BL	>20 increase from BL
	Hematocrit	%	L/L		
	Red blood cell count	10 ⁶ /uL	10 ¹² /L		
	White blood cell count	10 ³ /uL	10 ⁹ /L	<3	
	Platelet count	10 ³ /uL	10 ⁹ /L	<75	
	Mean corpuscular volume	fL	fL		
	Mean corpuscular hemoglobin	pg	pg		
	Mean corpuscular hemoglobin concentration	g/dL	g/L		
	Absolute neutrophils	10 ³ /uL	10 ⁹ /L	<1.5	
	Absolute lymphocytes	10 ³ /uL	10 ⁹ /L	<0.8	>4
	Absolute monocytes	10 ³ /uL	10 ⁹ /L		
	Absolute eosinophils	10 ³ /uL	10 ⁹ /L		
	Relative neutrophils	%	%		
	Relative lymphocytes	%	%		
	Relative monocytes	%	%		
	Relative eosinophils	%	%		
	Relative reticulocytes	%	%		

Category	Parameter	Conventional Unit	SI Units	PCI Criteria (SI units)	
				Low	High
Chemistry	Aspartate aminotransferase	U/L	U/L		>3xULN if BL did not exceed ULN, >3xBL if BL was above ULN
	Alanine aminotransferase	U/L	U/L		>3xULN if BL did not exceed ULN, >3xBL if BL was above ULN
	Creatinine	mg/dL	mcmol/L		>1.5xULN if did not exceed ULN, >1.5xBL if BL was above ULN
	Potassium	mEq/L	mmol/L		>5.5
	Sodium	mEq/L	mmol/L	<125	>150
	Blood urea nitrogen	mg/dL	mmol/L		
	Total bilirubin	mg/dL	mcmol/L		>1.5xULN if BL did not exceed ULN, >1.5xBL if BL was above ULN
	CRP	mg/L	nmol/L		
	Gamma-glutamyl transpeptidase	U/L	U/L		

Statistical Analysis Plan
Version 2.0, Final 16-Jan-2023

EDP1815-207

Category	Parameter	Conventional Unit	SI Units	PCI Criteria (SI units)	
				Low	High
Urinalysis	Protein	mg/dL	mg/dL		
	Blood				
	Glucose	mg/dL	mg/dL		
	Ketones	mg/dL	mg/dL		
	Bilirubin				
	pH	pH	pH		
	Nitrites				
	Specific gravity				

BL=Baseline, PCI = potentially clinically important, ULN = Upper limit of normal range.

Certificate Of Completion

Envelope Id: 745B2C54AFD341C299E23D85A1A54174
Subject: Complete with DocuSign: EDP1815-207 SAP V2.0 clean.pdf
Source Envelope:
Document Pages: 95

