8. EFFICACY ASSESSMENTS

Assessments will be performed at designated time-points throughout the study for efficacy evaluations. In addition to the assessments below, participants will provide information on their demographics and smoking history, past medical history (including diagnosis of atopic dermatitis), as well as concomitant medication usage.

All efficacy assessments will be completed at the study site utilizing a site tablet at the specified visits as indicated on the SOA. The site staff will assist the participant in completing those assessments that are considered patient reported outcomes (PRO). The same reviewer should conduct the skin assessments wherever possible for a single participant, and if not possible, at a minimum, the same reviewer performs the Day 1 and Week 16 assessments for that participant.

The Investigators and site staff will be provided with further details on how to perform the following assessments and how to calculate each of the scores (if applicable).

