5.3.3.7 Dermatology Life Quality Index (DLQI)

The DLQI is a 10-item questionnaire with each item scored from 0 to 3.

The DLQI score is the sum of the 10 individual items and ranges from 0 to 30, with higher scores indicating greater impairment of quality of life. Further information on the scoring of the DLQI is provided in [Section 20](#).

DLQI response is defined as a reduction of ≥ 4 in the DLQI score if a participant has a score of ≥ 4 at baseline (a 4-point change from baseline is considered the minimal clinically important difference threshold).

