7.3 Missing Data

Missing efficacy data such as individual item scores will be dealt with as detailed in [Section 5.3.3](#). Imputation of missing efficacy data due to intercurrent events will be performed in EDPS1, EDPS2, EDPS3, EDPS4 and EDPS5 as described in [Section 7.1.2](#).

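### The SAP scores every unanswered DLQI item as 0 with no limit on blanks, so two or more blanks after baseline can register as a false DLQI response

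*SAP*

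**What the plan says.** SAP Section 5.3.3.7 describes the instrument: "The DLQI is a 10-item questionnaire with each item scored from 0 to 3". The total "ranges from 0 to 30, with higher scores indicating greater impairment of quality of life". On the responder endpoint it says "DLQI response is defined as a reduction of ≥ 4 in the DLQI score", restricted to participants with a baseline score of at least 4.

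Appendix 6 holds the scoring rules. On missing items: "Any unanswered question is scored as 0". On the total: "The DLQI score is the sum of the 10 item scores". No number of blanks makes the form unscorable.

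Nothing elsewhere adds a limit. SAP Section 7.3 states "Missing efficacy data such as individual item scores will be dealt with as detailed in" Section 5.3.3, and the DLQI part of that section points on to Appendix 6. Protocol Section 8.5 has no missing-item rule, and the SAP's table of changes from the protocol does not mention one.

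The adjacent Appendix 5 treats the POEM differently. One blank is scored 0, but "If two or more questions are left unanswered the questionnaire is not scored".

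**The concern.** Higher DLQI is worse, so a blank scored 0 is recorded as no impairment on that item. With no cap, the more of a post-baseline form is left empty, the better the participant appears. The SAP limits this for the POEM and gives no reason for treating the DLQI otherwise.

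The endpoints affected are secondary: absolute and percentage change from baseline (SAP Section 9.4.1) and the 4-point response (Section 9.4.2), at Weeks 4, 8, 12 and 16, each reported with p-values against placebo.

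The rule also sits awkwardly with EDPS1. There, a DLQI missing for reasons unrelated to study medication stays missing, and one missing through related withdrawal is a non-response. A form returned with many blanks can instead count as a response.

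**Working it through.** **Inputs.** Ten items scored 0 to 3, summed (SAP Section 5.3.3.7 and Appendix 6); blank = 0 (Appendix 6); response = fall of at least 4 from a baseline of at least 4 (Section 5.3.3.7).

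**Check of the plan's own figure.** 10 × 3 = 30, which matches the stated maximum.

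**Formula.** Take a complete baseline and no true change. If a set B of items is left blank later, the recorded fall is the sum of the true values of the items in B. With k blanks it cannot exceed 3k.

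- k = 1: maximum fall 3, below 4, so no false response.
- k = 2: maximum fall 6, so a false response is possible.

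**Uniform profiles.**

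| True item values | True score | Blanks | Recorded score | Fall |
|---|---|---|---|---|
| all 1 | 10 | any 3 | 7 | 3 (no response) |
| all 1 | 10 | any 4 | 6 | 4 (response) |
| all 2 | 20 | any 2 | 16 | 4 (response) |
| all 3 | 30 | any 2 | 24 | 6 (response) |

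**A mixed profile (assumed).** Items 3, 2, 2, 1, 1, 1, 1, 1, 0, 0 sum to 12. There are 45 ways to leave two blank. A fall of 4 or more needs the 3 with a 2 (2 ways), the 3 with a 1 (5 ways) or both 2s (1 way): 8/45 = 18%. Counting all patterns in the same way gives 52% with three blanks, 81% with four, 96% with five and 100% with six or more.

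**Low baseline (assumed).** Four items at 1 and six at 0 give a score of 4. Even with eight blanks, only 33% of patterns remove all four points (15 of 45).

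**True worsening.** If all items go from 2 to 3, the true score rises from 20 to 30. With five blanks the recorded score is 5 × 3 = 15, a fall of 5 and a response.

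**Blanks at baseline.** The direction reverses. A true 20 (all items at 2) with two blanks is recorded as 16, so a true improvement to 16 shows as no change. A true 5 with two items of value 1 blank is recorded as 3, and the participant drops out of the responder endpoint.

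**With the POEM limit applied to the DLQI.** At most one item can be set to 0, so the largest artificial fall is 3, below the threshold of 4.

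**The case against.** **Collection mode.** Protocol Section 8 says "All efficacy assessments will be completed at the study site utilizing a site tablet", with staff helping on patient-reported outcomes, and Section 10.2.1 keeps paper for unforeseeable failures of the electronic source. This probably makes multiple blanks uncommon, and it stands as a limit on the size of the problem. It does not remove it: mandatory items are not stated, paper is permitted, and the SAP itself provides for unanswered items.

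**Zero as "not relevant".** Questions 3 to 10 also score 0 for that answer, so a skipped item might mean it. This has some force for a single blank. But the form already offers the option explicitly on those items, and questions 1 and 2 do not have it.

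**The POEM comparison.** One blank POEM item can remove 4 points, which equals the POEM response threshold, so that rule is not airtight on its own scale. A limit of one is also borrowed, since the documents state none for the DLQI. Both points are fair. The limit does work on the DLQI, because one DLQI item carries at most 3 points.

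**Stronger readings that the documents do not support.**

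- A reader might infer that missing answers become treatment benefit. The rule is the same in every arm and treatment within cohort is blinded. Nothing suggests that blanks would differ by arm; if they do not, false responses arise on both sides.
- A reader might infer that a wholly blank form scores 0 and makes anyone with a baseline of 4 or more a responder. Appendix 6 speaks of an unanswered question. A form with no answers can equally be read as an assessment not done, which Protocol Section 7.12 handles as a deviation at Day 1 and Week 16 and EDPS1 generally leaves missing.
- A reader might scale a score of 12 by 6/10 and say that four blanks give 7.2, a fall of 4.8 and hence a response. That is an average over patterns. Real scores are whole numbers, and in the mixed profile above 19% of four-blank patterns do not reach the threshold.

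**Conclusion.** The point holds as a minor flaw in a stated rule. Followed as written, Appendix 6 can turn two or more post-baseline blanks into a false response, and blanks at baseline can hide a real one. Whether it does so depends on how many items are blank and what their true values are.

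The consequence is misclassification in the secondary DLQI change and responder endpoints. Bias between arms requires blanks to differ by arm. The primary EASI-50 analysis is untouched. The overall size cannot be stated because the documents give no rate of unanswered items. The profile percentages are illustrations that assume every pattern of blanks is equally likely.

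**What to change.** Amend Appendix 6 so that one unanswered DLQI item is scored 0 and, with two or more unanswered at any visit including baseline, the DLQI is not scored and is handled as missing under the applicable data point set. State this before the data concerned are unblinded; the SAP allows Cohorts 1-3 to be unblinded ahead of Cohort 4, so the deadline differs between them. Where unblinding has already happened, run it as a labelled sensitivity analysis.

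The cost is one sentence and a few incomplete forms becoming missing. An unscored baseline costs more than an unscored visit: the schedule collects the DLQI first on Day 1, so there is no screening value to fall back on and that participant leaves the DLQI change and responder analyses.

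The change is not complete protection. One blank can still add up to 3 points to a true fall of 1, or take a true baseline of 6 down to 3. It does ensure that post-baseline blanks alone cannot make an unchanged participant with a complete baseline a responder.
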